9.2.4.2 Patient selection

Following site activation and staff training, the site staff will compile a patient roster from their prescription records according to the eligibility period.

For sites with more than 8 potential eligible patients, sites are asked to list their potential patients and assign them each a consecutive number. The CRO will use a random selection tool that randomly orders the previously consecutive numbers and instructs the sites which numbers were ranked as top 8. The site will look back at their list of patients and will enroll the patients with the assigned numbers that were ranked as the top 8. Should any of these 8 patients not be eligible for enrollment, the patient assigned to the next number (ie, ranked 9th) from the randomization tool will be approached.

When required by local regulation, site staff will contact patients for consent. The site might be facing the following scenarios:

- Remote consent for the patients who are not scheduled to return to the office within 1 month time. The site will contact the patient by phone to explain the study and will send the Informed Consent Form (ICF) to the patients who have interest to return, signed and dated. Patients will have the opportunity to ask questions over the phone and they will be able to decide freely if they wish to participate.
- Face to face consent for patients who will return to the office within 1 month. The ICF will be signed and dated during this visit.

Site staff will keep a patient log to track anonymous information on the patients who refuse to participate (please see Section 9.6.4).

For each participating physician, up to 8 patients will be randomly enrolled. If the number of patients treated by physician is less than 8, no random selection will be needed. If there are 2 physicians from the same practice/institution participating in the same wave of the study, the combined total number of patients selected from these 2 physicians will be limited to 10 and a random selection of 10 patients will be performed.

Patients who have participated in any randomized clinical trials of Praluent (alirocumab) will be excluded from this study.

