9.7.1 Primary analysis

Descriptive analyses will be conducted for each wave separately. In addition, analyses will be conducted using the entire data of all 3 waves.

Point estimates of proportions and 95% confidence intervals will be calculated.

Data will be summarized using mean, first quartile, median, third quartile, standard deviation and range for continuous parameters and counts, percentages and 95% confidence intervals if needed for categorical parameters. The analyses will be performed, overall, by countries, and for specific analyses (starting dose of Praluent, occurrence of very low LDL-C level) will also be presented based on baseline LDL-C levels.

The following descriptive analyses will be presented on the eligible population:

A. Occurrence of very low LDL-C level

An LDL-C level <25 mg/dL (0.65 mmol/L) is defined as very low; and an alternative definition with a cut-off at 15 mg/dL (0.39 mmol/L) will also be used.

For each definition of very low LDL-C level, the following statistics will be calculated:

- 1. The proportion of patients who have at least 1 very low LDL-C level during the 6-month observational period:
 - (1) In the whole analysis population,
 - (2) According to baseline LDL-C level (<70; 70 to <100; 100 to <130; 130 to <160; 160 to <190; ≥190 mg/dL),
 - (3) According to Praluent starting dose.
- 2. All occurrences of very low LDL-C levels will be classified according to the Praluent regimen received at the time of the corresponding LDL-C test.

B. Evolution of LDL-C level after the occurrence of very low LDL-C level

- 1. Among the patients who have a LDL-C level of <25 mg/dL (0.65 mmol/L) at any dose, the proportions of patients whose LDL-C level returns to ≥25 mg/dL (0.65 mmol/L) within 8 weeks after the lab test, if data available, and at any time until the end of the 6-month observational period after index date, respectively.
 - (1) Overall,
 - (2) By the action of dosage regimen modification or discontinuation of Praluent, or change in dosing frequency of Praluent, or lowering doses of other lipid-lowering drugs, or discontinuation of other lipid-lowering drugs.
- 2. Same analysis will be conducted for the patients who have LDL-C level <15 mg/dL (0.39 mmol/L).

C. Change in treatment after the occurrence of very low LDL-C level

For each definition of very low LDL-C level, the following statistics will be calculated:

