9.7.3 Sensitivity analysis regarding the physicians selection

Physicians who are/were involved in an observational study on Praluent are allowed to participate in this study. If these physicians provided at least 15% of the patients in this study then, to assess if this constitutes a bias, all analyses will be conducted separately in patients who were managed by them and in patients who were managed by physicians who had never participated in an observational study on Praluent.

The MAH plans to assess the representativeness of study sample with respect to the level of prescription a posteriori in the analysis phase. This analysis will stratify data by physician usage patterns to understand how they might impact dosing recommendations and assess the effectiveness of the Praluent dosing recommendations with regard to the occurrence of low LDL-C levels and will consist of:

a) The MAH will be collecting information on the level of prescription via a case report form (CRF) on the enrolled physicians. The final selected study sample of Praluent prescribers will be compared to the population of Praluent prescribers

identified from the Xponent or equivalent databases, with respect to the level of prescription.

- b) If the groups (ie, high, medium or low prescribers) are not balanced in a similar way, and if representativeness cannot be assumed, results will be presented by stratifying the level of prescription in each interim report and the final study report.
- c) As deemed appropriate, statistical techniques will be applied in the analysis phase to ensure the groups are representative with respect to the level of prescription.

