9.9 LIMITATIONS OF THE RESEARCH METHODS

Selection bias

Potential limitations of the study design include physicians' enrollment bias. It is likely that physicians who participate in this study may be different from those who do not with respect to specialty. It is anticipated that specialists are more likely to participate. Efforts will be made to ensure an appropriate representation of physician specialty in the study.

A random selection of patients at the practice level will alleviate potential selection bias and limit notably channeling bias.

The clusters and physicians that have the highest likelihood of having prescribed Praluent and of participating in the study will be contacted regardless of their level of prescription. Representativeness of study sample with respect to the prescription level will be assessed a posteriori in the analysis phase (Section 9.7.3).

In order to avoid bias due to the awareness of the study objectives, a different group of physicians that has not participated in any previous waves of the study will be selected.

The quality of medical charts review

As this study involves multiple physicians from different countries, the quality and quantity of medical information available from medical charts may vary by clinics and hospitals. Additionally, medical charts may not be obtained from all patients or physicians. Data availability on 6-month observation period, in particular availability of critical variables, will be secured at the time of site selection through a questionnaire.

Strategies to prevent missing data will be put in place, such as:

- Collecting only critical data elements to minimize site burden.
- Including "not applicable" and "not done" on case report forms to differentiate those from values that are truly unknown.

- Training of sites and data abstractors regarding data collection.
- Checking for pattern of missing data at regular intervals and addressing any issues with targeted operational strategies.

Medical chart review will be conducted to abstract data; as such there will be no direct patient contact involved.

Data from the observational period will be collected in a retrospective way. The retrospective approach avoids influencing physicians in their prescribing behavior as only patients already treated with Praluent will be considered. No guidance on treatments is given in the study protocol.

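### The 9.7.3 representativeness check compares prescribers, but the primary estimate counts patients under a cap of 8 per physician, so a balanced physician mix does not ensure a balanced patient mix

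*Protocol*

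**What the plan says.** Three parts of the protocol bear on this.

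- **The estimate (9.7.1 A.1).** The first primary statistic is "The proportion of patients who have at least 1 very low LDL-C level during the 6-month observational period", in the whole analysis population, by baseline LDL-C and by starting dose. No weights are mentioned.
- **Patient sampling (9.2.4.2).** "For each participating physician, up to 8 patients will be randomly enrolled". Smaller rosters are taken without sampling. A random selection tool is provided "For sites with more than 8 potential eligible patients". Where two physicians of one practice take part in a wave, "the combined total number of patients selected from these 2 physicians will be limited to 10".
- **The check (9.7.3).** Item a): "The final selected study sample of Praluent prescribers will be compared to the population of Praluent prescribers" found in the prescription database, with respect to level of prescription. Item b) presents results by prescription level on a condition: "If the groups (ie, high, medium or low prescribers) are not balanced in a similar way, and if representativeness cannot be assumed". Item c) adds that, where judged appropriate, "statistical techniques will be applied in the analysis phase to ensure the groups are representative with respect to the level of prescription". The lead-in to a)-c) says that data will be stratified by physician usage pattern and links this to the occurrence of low LDL-C.

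Section 9.9 relies on sampling within practices: "A random selection of patients at the practice level will alleviate potential selection bias".

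**The concern.** The check and the estimate use different units. A matching mix of physicians implies a matching mix of patients only if each physician contributes patients in proportion to caseload, and the cap prevents that. Among participating physicians, and before refusals, a patient on a roster of 8 or fewer is taken with probability 1. A patient on a roster of N > 8 is taken with probability 8/N. Random choice within a practice keeps that practice's patients representative of that practice. It does nothing for the balance between practices.

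The check carries weight because random selection of physicians was dropped (Annex 3, Amended Protocol 01) and the a posteriori comparison was put in its place. Section 9.7.3 itself treats prescribing level as something that may bear on low LDL-C. If it does, a sample that passes the physician comparison can still give a pooled proportion tilted towards patients of smaller prescribers, and nothing in a)-c) would reveal it. The eligibility window also went from 4 months in Wave 1 to 12 months in Waves 2 and 3, which makes rosters above 8 more likely in the later waves. Any distortion may therefore differ by wave, while 9.2.1 makes comparison across waves an aim.

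**Working it through.** **Stated precision.** Exact (Clopper-Pearson) 95% limits for an observed 5%:

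- N = 454: 3.19 to 7.43, half-width 2.12 (protocol 9.5.1: 2.1).
- N = 574: 3.37 to 7.11, half-width 1.87 (protocol: 1.85, which is (7.1 - 3.4)/2 from the rounded limits).

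The plan's figures reproduce.

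**How often can the cap bind?** Mean enrolment was 68/20 = 3.4 per site in Wave 1 and 251/61 = 4.1 in Wave 2. If k sites enrolled 8 and every other site at least 1, then 8k + (20 - k) ≤ 68 gives k ≤ 6, and 8k + (61 - k) ≤ 251 gives k ≤ 27. With one physician per site, at most 6 of 20 and 27 of 61 sites reached 8. The true number is not given and could be small.

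**Effect with a perfectly matched physician mix.** Let f be the fraction of physicians at each level and s the eligible patients per physician.

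- Population patient share = f·s / Σ(f·s)
- Sample patient share = f·min(s, 8) / Σ(f·min(s, 8))
- Each proportion = Σ(share × rate)

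The protocol gives neither s nor rates by level, so both are assumptions, as is the premise that high prescribers are those with large rosters. Take f = 40/40/20% (low/medium/high) and s = 2/4/16.

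- Population: f·s = 0.8, 1.6, 3.2 (sum 5.6), shares 14/29/57%.
- Sample: 0.8, 1.6, 1.6 (sum 4.0), shares 20/40/40%.

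The mean of 4.0 per site is close to the observed 3.4 and 4.1, and 20% of sites at the cap (4 of 20, about 12 of 61) is within the bounds above.

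| f (%) | s | Rates (%) | High share, population → sample | True | Sample | Bias (points) |
|---|---|---|---|---|---|---|
| any | none above 8 | any | unchanged | – | – | 0 |
| any | any | equal | – | – | – | 0 |
| 40/40/20 | 2/4/12 | 4/5/6 | 50% → 40% | 5.33 | 5.20 | -0.13 |
| 40/40/20 | 2/4/16 | 8/5/2 | 57% → 40% | 3.7 | 4.4 | +0.7 |
| 40/40/20 | 2/4/16 | 2/5/8 | 57% → 40% | 6.3 | 5.6 | -0.7 |
| 40/40/20 | 2/4/30 | 8/5/2 | 71% → 40% | 3.1 | 4.4 | +1.3 |
| 40/40/20 | 2/4/30 | 2/5/8 | 71% → 40% | 6.9 | 5.6 | -1.3 |
| 50/30/20 | 2/5/40 | 3/5/10 | 76% → 39% | 8.62 | 6.46 | -2.16 |

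**Would adjusting to the physician mix help?** Not necessarily. Keep s = 2/4/16, and suppose high prescribers were over-recruited so that the sample mix is 35/35/30%. Contributions are 0.7, 1.4, 2.4 (sum 4.5), so high prescribers supply 2.4/4.5 = 53% of patients against 57% in the population. Re-weighting physicians back to 40/40/20 gives 0.8, 1.6, 1.6, or 40%. The adjustment moves the patient mix further from the population.

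**Price of roster weights.** Weights are 1 below the cap and s/8 above it. The Kish design effect is n·Σw²/(Σw)². For f = 50/30/20 and s = 2/5/16: 4.1 × 8.9/5.7² = 1.12, an effective size of about 404 of 454. For s = 2/5/24: 4.1 × 16.9/7.3² = 1.30, about 349 of 454.

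**The case against.** The strongest reply has four parts.

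1. **The lead-in and item c).** The lead-in announces stratification by usage pattern with low LDL-C in view, and item c) leaves room for weighting. It would be wrong to infer that 9.7.3 ignores LDL-C outcomes or excludes adjustment. But item b) makes stratified presentation depend on imbalance among physicians, and item c) is optional and aimed at prescription level. A sample with a balanced physician mix is promised neither.
2. **This belongs in the SAP.** Section 9.7 says that it gives specifications for a SAP, and the choice of weights can properly sit there. What the protocol itself fixes is the unit of comparison, prescribers. A volume-based comparison is possible, since 9.2.4.1 draws prescribing volume from the database, but 9.7.3 does not commit to one.
3. **Purpose.** The section addresses physician selection and was not written to audit patient sampling. That is fair. But no other part of the protocol covers the cap, and the reassurance in 9.9 reaches only within practices.
4. **Materiality.** All roster sizes and rate gradients above are assumed. The protocol reports low prescribing in Wave 1, and means of 3.4 and 4.1 per site are compatible with few or no rosters above 8. This stands in full.

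Two further readings lack support. A reader might infer that the report will declare the sample representative whenever the physician mix matches; the protocol does not say so. Nor are 1 and 8/N overall selection probabilities: they hold only given physician participation, eligibility and, where required, consent, and physicians are not recruited at random.

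**Conclusion.** The design point holds: a comparison of prescribers cannot show whether patients are represented in proportion once enrolment is capped per physician, and nothing in 9.7.3 ensures a correction when the physician mix looks balanced. Under-representation of patients on rosters above the cap follows from the sampling rule, given physician participation and similar consent across sites.

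Whether this biases the primary proportion is open. Bias requires both rosters above the cap and rates of very low LDL-C that differ by prescription level, and the documents establish neither its size nor its sign. A reader might infer that the primary result is known to be biased; the documents do not show that. In the assumed scenarios the error runs from zero, through 0.1 to 1.3 points, to about 2.2 points in the extreme case. That is from negligible to as large as the stated half-width, which does not include it. This calls for an inexpensive sensitivity analysis and does not show the primary analysis to be invalid.

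**What to change.** 1. In 9.7.3 a)-b), also compare the share of Praluent-initiated patients, or of prescription volume, by prescription level between sample and database.
2. Record the number of eligible patients on each site's roster. Sites already compile a roster under 9.2.4.2, and it is numbered where random selection is used.
3. As a sensitivity analysis in every report, whether or not the physician mix is balanced, give the primary proportion with each patient weighted by eligible roster size over patients enrolled, next to the unweighted figure. Use the practice roster where the limit of 10 applies.
4. State the limits: the weights correct the cap only, not the non-random selection of physicians, and they treat non-consent as random within a site.

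The cost is a short change to 9.7.3 or the SAP, one variable per site and one extra table. The weighted interval would be somewhat wider: a design effect of 1.1 to 1.3 widens it by a factor of about √1.1 = 1.05 to √1.3 = 1.14.

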9.7.4 Interim analysis

A separate descriptive analysis will be performed for each wave separately (1, 2, and 3) once the 6-month observation period data have been retrospectively collected, so that any potential concern can be addressed earlier.

In addition, analyses will be conducted using all the data obtained from the 3 waves and will be included in the final report.

9.8 QUALITY CONTROL

9.8.1 Data collection, validation and data quality control at MAH/CRO delegated by the MAH level

Data will be collected using electronic CRF. The e-CRFs will be completed directly by site personnel and/or by a trained external medical record abstractor through a secure, easy to use and reliable web-based electronic data capture (EDC) platform. As an optional service requested by sites or as required to complete data abstractions within the defined time period, it is assumed that the CRO delegated by the MAH will perform data abstractions visits.

The computerized handling of the data by the MAH after receipt of the CRFs may generate additional requests to which the participating physician is obliged to respond by confirming or correcting the data questioned in the EDC. The requests with their responses will be appended to the CRFs held by the physician and the MAH.

Additional details regarding data collection and validation procedures will be detailed in appropriate operational documents.

9.8.2 Data quality control at site level

Type of data quality control (monitoring visit and/or phone QC) and the percentage of the sites that will be controlled are developed in this section.

Initiation visits: once all regulatory approvals and contracts are in place, a remote initiation visit per site will be conducted. Sites will be trained on the study protocol and procedures during this visit.

Monitoring visits: the monitoring approach employs a combination of remote and for cause monitoring visits in case quality risks are identified (eg, missing data, delays in entering the data in the system, delay in answering queries).

Data QC will be performed in 10% of the active sites (which have enrolled at least one patient) chosen at random in each country. If specific issues are identified in some sites or countries (see above), the percentage of QC in the concerned site/country or in all sites/countries must be appropriately increased and corrective actions must be set up.

Quality control will be performed by qualified designated personnel in each country.

The methodology of data QC and appropriate consecutive corrective actions will be detailed in the study manual.

9.9 LIMITATIONS OF THE RESEARCH METHODS

Selection bias

Potential limitations of the study design include physicians' enrollment bias. It is likely that physicians who participate in this study may be different from those who do not with respect to specialty. It is anticipated that specialists are more likely to participate. Efforts will be made to ensure an appropriate representation of physician specialty in the study.

A random selection of patients at the practice level will alleviate potential selection bias and limit notably channeling bias.

The clusters and physicians that have the highest likelihood of having prescribed Praluent and of participating in the study will be contacted regardless of their level of prescription. Representativeness of study sample with respect to the prescription level will be assessed a posteriori in the analysis phase (Section 9.7.3).

In order to avoid bias due to the awareness of the study objectives, a different group of physicians that has not participated in any previous waves of the study will be selected.

The quality of medical charts review

As this study involves multiple physicians from different countries, the quality and quantity of medical information available from medical charts may vary by clinics and hospitals. Additionally, medical charts may not be obtained from all patients or physicians. Data availability on 6-month observation period, in particular availability of critical variables, will be secured at the time of site selection through a questionnaire.

Strategies to prevent missing data will be put in place, such as:

- Collecting only critical data elements to minimize site burden.
- Including "not applicable" and "not done" on case report forms to differentiate those from values that are truly unknown.

- Training of sites and data abstractors regarding data collection.
- Checking for pattern of missing data at regular intervals and addressing any issues with targeted operational strategies.

Medical chart review will be conducted to abstract data; as such there will be no direct patient contact involved.

Data from the observational period will be collected in a retrospective way. The retrospective approach avoids influencing physicians in their prescribing behavior as only patients already treated with Praluent will be considered. No guidance on treatments is given in the study protocol.

9.10 OTHER ASPECTS

Not applicable.

10 PROTECTION OF HUMAN SUBJECTS

10.1 RESPONSIBILITIES OF THE HEALTH CARE PROVIDERS

The Health Care Provider will perform the study in accordance with this protocol, applicable local regulations and international guidelines.

It is the Health Care Provider's responsibility to obtain written informed consent from patients prior to inclusion in the study, to fill in the CRF and to record all data pertinent to the investigation. She/he will ensure that the information reported in the CRF is precise and accurate. Where allowed and feasible, a trained external medical record abstractor can also complete the e-CRFs through a secure, easy to use and reliable web-based EDC platform.

Health Care Provider, and under the Health Care Provider's responsibility, should fully inform the patient of all pertinent aspects of the study including the written information. All patients should be informed to the fullest extent possible about the study, in language and terms they are able to understand.

Prior to a patient's retrospective data collection, the written ICF has to be signed, name filled in and personally dated by the patient or by the patient's legally acceptable representative, and by the person who conducted the informed consent discussion. A copy of the signed and dated written ICF will be provided to the patient.

The ICF and the Information Sheet used by the Health Care Provider for obtaining the Patient's Informed Consent must be reviewed and approved by the MAH/CRO delegated by the MAH prior to submission to the appropriate Institutional Review Board/Independent Ethics Committee (IRB/IEC) for approval/favorable opinion.

